1.0 Introduction and Background

In 2011, liposomal bupivacaine received FDA approval for the use of local surgical site infiltration, and its use has become common for a variety of abdominal, gynecological, and orthopedic surgeries, with varying efficacy.^{1,2,3} Studies evaluating the efficacy of liposomal bupivacaine for regional procedures have also displayed mixed results.⁴

Liposomal bupivacaine has recently been approved by the FDA for use in brachial plexus blocks for patients undergoing major shoulder surgery.⁵ Per the manufacturer's data, ISB using liposomal bupivacaine provided significant pain reduction in the first 48 hours after surgery compared to ISB using placebo, establishing that liposomal bupivacaine has an opioid sparing effect in this patient population without significant risk.

A recent study compared the addition of liposomal bupivacaine to plain bupivacaine for interscalene blocks in patients undergoing shoulder surgery, and found a modest improvement in pain.⁶

At a cost of about \$300 per administration for liposomal bupivacaine, there are significant economic impacts to be considered, given that plain bupivacaine is significantly less expensive. Data from future studies are required to perform a cost-benefit analysis for this new drug.

Common and relatively inexpensive adjuvants have been shown to extend the duration of analgesia provided by interscalene nerve blocks (ISB) using plain bupivacaine, with a significant analgesic effect extending up to 48 hours postoperatively.⁷⁻⁹

To date, there has been no study comparing the efficacy of ISB using liposomal bupivacaine vs plain bupivacaine with these common adjuvants, such as epinephrine, dexamethasone, clonidine, and buprenorphine.

The purpose of this study is to determine whether the use of plain bupivacaine with common adjuvants for ISB provides non-inferior analgesic results compared to the use of liposomal bupivacaine for ISB, in patients undergoing primary total shoulder arthroplasty.

LB= Liposomal bupivacaine

PBA= Plain bupivacaine + adjuvants

ISB= Interscalene peripheral nerve block

Single Injection interscalene brachial plexus nerve block with adjuvants vs. Liposomal bupivacaine
interscalene brachial plexus nerve block for total shoulder arthroplasty

2.0 Objectives

2.1 Primary Objective(s)

- 2.1.1 The primary objective of this clinical study is to evaluate the comparative efficacy of ISB using plain bupivacaine with adjuvants vs. liposomal bupivacaine on mean postoperative pain levels in patients who have undergone shoulder arthroplasty within the first 48 hours. We hypothesize that ISB using plain bupivacaine with adjuvants will provide similar pain relief as ISB using liposomal bupivacaine.

2.2 Secondary Objective(s)

- 2.2.1 To evaluate the effect of ISB using plain bupivacaine with adjuvants vs. liposomal bupivacaine on pain control at the single time point of 48 hours post-surgery.
- 2.2.2 To evaluate the effect of ISB using plain bupivacaine with adjuvants vs. liposomal bupivacaine on cumulative postoperative opioid consumption within the first 48 hours after shoulder arthroplasty.

Single Injection interscalene brachial plexus nerve block with adjuvants vs. Liposomal bupivacaine
interscalene brachial plexus nerve block for total shoulder arthroplasty

3.0 Patient Selection

3.1 Inclusion Criteria

- 3.1.1 All patients undergoing primary total shoulder arthroplasty
- 3.1.2 Age \geq 18 years
- 3.1.3 Ability to understand and the willingness to sign an IRB-approved informed consent document.
- 3.1.4 ASA patient status I-III patients
- 3.1.5 Weight Greater than or equal to 50 kg

3.2 Exclusion Criteria

- 3.2.1 No contraindications to an interscalene block or phrenic blockade.
- 3.2.2 Infection at injection site.
- 3.2.3 Pre-existing neurological dysfunction affecting the operative extremity.
- 3.2.4 Chronic pain diagnosis or opioid use >40 mg oxycodone daily equivalents or use of long-acting opioids.
- 3.2.5 BMI >40
- 3.2.6 Uncontrolled diabetes (A1c >8.0)
- 3.2.7 Concurrent painful physical condition requiring analgesic treatment (eg, NSAID or opioid) in the postsurgical period for pain not strictly related to the surgery
- 3.2.8 Contraindications to any pain-control agents planned for surgical or postsurgical use (i.e., bupivacaine, hydromorphone, etc.)
- 3.2.9 Patients who are wards of the state
- 3.2.10 History of allergic reactions attributed to compounds of similar chemical or biologic composition to bupivacaine or liposomal bupivacaine.
- 3.2.11 Patients with moderate-severe hepatic or renal impairment because of the increased risk of toxicity.
- 3.2.12 Patients who are pregnant.
- 3.2.13 Patients who are lactating.
- 3.2.14 Patients with hypersensitivity to any of the study drugs, including dexamethasone, clonidine, and buprenorphine.
- 3.2.15 Patients with labeled contraindications for the study drugs, such as systemic fungal infections.
- 3.2.16 Patients undergoing repeat shoulder arthroplasty or reverse total shoulder arthroplasty.

Single Injection interscalene brachial plexus nerve block with adjuvants vs. Liposomal bupivacaine interscalene brachial plexus nerve block for total shoulder arthroplasty

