4.2 Secondary Outcomes

- 4.2.1 Mean VAS-NRS pain score at 48 hours.
 - 4.2.1.1 For patients undergoing ISB with liposomal bupivacaine, the mean VAS pain score at 48 hours was 3.39 with a standard error of 0.37.¹⁰
 - 4.2.1.2 There are no existing data to predict the mean VAS pain score at 48 hours for patients undergoing ISB with plain bupivacaine + adjuvants, however a similar study using plain bupivacaine alone demonstrated a mean NRS (similar to VAS) pain score of 5.5 with standard error +/-0.5⁶. We expect the mean pain score to be slightly below this value, approximately 4.5.
- 4.2.2 Postoperative opioid consumption
 - 4.2.2.1 The mean rescue opioid consumption (in IV morphine equivalents) in the first 48 hours after receiving ISB using liposomal bupivacaine was 12.0 +/- 2.3 in a previous study.¹⁰
 - 4.2.2.2 We expect the patients treated with plain bupivacaine and adjuvants to use a similar average of 12.0 intravenous morphine equivalents in the first 48-hours following surgery. For the purpose of this study, we will convert IV morphine equivalents to oral codeine equivalents.
- 4.2.3 Satisfaction with surgical experience
 - 4.2.3.1 At the 48 hour mark, the patient's satisfaction with the surgical experience, satisfaction with pain control, and willingness to recommend the procedure to another patient will be assessed via Likert scale. Adverse events will also be evaluated.

Single Injection interscalene brachial plexus nerve block with adjuvants vs. Liposomal bupivacaine interscalene brachial plexus nerve block for total shoulder arthroplasty

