6.2 Analysis of Secondary Objectives

- 6.2.1 For the mean VAS-NRS score at 48 hours, prior studies have found an average score of 3.8 with a standard deviation of 2.88 (standard error of 0.36) for ISB using liposomal bupivacaine.¹⁰ There have been no studies to evaluate the pain scores after ISB using plain bupivacaine with adjuvants. This study will be powered to detect a difference of at least 0.4 on the VAS-NRS scale. We will define the threshold for inferiority as a difference of ≥ 2 points on the VAS scale. Analysis will be conducted using a two-sample t test with $\alpha = 0.05$ and $\beta = 0.1$.
- 6.2.2 For the comparison of post-operative opioid consumption, each patient's total post-operative opioid usage during the first 48 hours will be converted to oxycodone equivalents. The geometric mean opioid consumption for each cohort will be calculated, and the two cohorts will be compared for statistical difference using a two-sample t test, with $\alpha = 0.05$ and $\beta = 0.1$.
- 6.2.3 Patient satisfaction will be assessed on POD#2 by 5-point Likert rating scale, and via a binary question of "would you recommend this pain relief regimen to the next patient". The results of these questions will be compared with a Fisher's Exact Test, with $\alpha = 0.05$.

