Appendix A- Eligibility Checklist

| | | |
|--------------------------------------------------------------------------------------------------------------------------------------------------------------------------------------------------------|--------------------|--|
| IRB Protocol No. 00055981 | SUBJECT ID: | |
| Study Title: SINGLE INJECTION INTERSCALENE BRACHIAL PLEXUS NERVE BLOCK WITH ADJUVANTS VS. LIPOSOMAL BUPIVACAINE INTERSCALENE BRACHIAL PLEXUS NERVE BLOCK FOR TOTAL SHOULDER ARTHROPLASTY | | |
| Principal Investigator: [name], D.O. | | |

| Inclusion Criteria (as outlined in study protocol) | Criteria is met | Criteria is NOT met | Source Used to Confirm * (Please document dates and lab results) |
|------------------------------------------------------------------------------------------------------------------------------|-------------------------------------|--------------------------------|-----------------------------------------------------------------------------------|
| All patients who are undergoing total shoulder arthroplasty |  |  | |
| Age >18 years |  |  | |
| Ability to understand and willingness to sign IRB-approved informed consent document |  |  | |
| Weight Greater than or equal to 50 kg |  |  | |
| ASA patient status I-III |  |  | |
| Exclusion Criteria (as outlined in study protocol) | Criteria NOT present | Criteria is present | Source Used to Confirm * (Please document dates and lab results) |
| No contraindications to an interscalene block or phrenic blockade. |  |  | |
| Infection at injection site. |  |  | |
| Pre-existing neurological dysfunction affecting the operative extremity. |  |  | |
| Patients who abuse narcotics or have chronic pain (using greater than 40 mg equivalents of oxycodone per day) |  |  | |
| Patients who are wards of the state |  |  | |
| BMI >40 |  |  | |
| Uncontrolled diabetes (HbA1c >8.0) |  |  | |

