Appendix H- Data Collection Form

| | |
|--------------|-----------------------------------------|
| | Assigned Study Number: |
| | WakeOne MRN |
| Demographics | Age |
| | Sex |
| Procedure | Comorbidities |
| | Pre-surgical analgesics |
| Medical Hx | Preop pain score |
| | Pre-op multimodal analgesics |
| | Post-Block assessment |
| Pre-Op | Intra-op Narcotics (PO oxy equivalents) |
| | Pain score in PACU p/t discharge |
| Intraop | PACU block assessment |
| | PACU opioids (PO oxy equivalents) |
| | +6hr worst pain score (VAS) |
| PACU | |
| | |

Single Injection interscalene brachial plexus nerve block with adjuvants vs. Liposomal bupivacaine interscalene brachial plexus nerve block for total shoulder arthroplasty

| | |
|------------------|-----------------------------------------------------------------------------------------------------------------------------------------------------------------------------------------------------------------------------------------------------------------------------------------------------------------------------------------------------------------------------------------------------------------------------------------------------------------------------------------------------------------|
| | 
+12h worst pain score (VAS)
 
+24h worst pain score (VAS)
 
+36h worst pain score (VAS)
 
+48h worst pain score (VAS)
 
+6hr opioid use (PO oxy eq)
 
+12h opioid use (PO oxy eq)
 
+24h opioid use (PO oxy eq)
 
+36h opioid use (PO oxy eq)
 
+48h opioid use (PO oxy eq)
 
Likert Satisfaction #1
 
Likert satisfaction #2 Nonopiod Analgesics Used Side effect evaluation (Itching, Nausea/vomiting)
 |
| Post OP | |
| Off study | 
("OFF" if applicable)
 
Reasons:
 |

Date of study completion:

Evaluable subject?

Protocol deviations?

Single Injection interscalene brachial plexus nerve block with adjuvants vs. Liposomal bupivacaine interscalene brachial plexus nerve block for total shoulder arthroplasty

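### The 48 h opioid comparison makes no use of pre-operative opioid intake, although users of up to 40 mg oxycodone a day may enrol and the data form already records prior analgesics; the cost is precision, not bias.

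*Combined protocol and SAP*

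**What the plan says.** - **Eligibility.** Protocol 3.2.4 excludes "Chronic pain diagnosis or opioid use >40 mg oxycodone daily equivalents or use of long-acting opioids". Exclusion 3.2.7 removes patients with a "Concurrent painful physical condition requiring analgesic treatment (eg, NSAID or opioid) in the postsurgical period for pain not strictly related to the surgery". Neither criterion removes a patient who takes a short-acting opioid at or below the limit for the shoulder being replaced. The Appendix A checklist words the first criterion differently: "Patients who abuse narcotics or have chronic pain (using greater than 40 mg equivalents of oxycodone per day" (closing bracket omitted here). It ties chronic pain to the 40 mg limit and is therefore looser than 3.2.4.
- **Outcome.** Under 6.2.2, "each patient's total post-operative opioid usage during the first 48 hours will be converted to oxycodone equivalents". No rule separates usual intake from new use.
- **Analysis.** Section 6.2.2 names geometric means and a two-sample t test, with no covariate. Section 5.1 describes computer randomisation and names no stratification factor.
- **Expected level.** For the liposomal arm, 4.2.2.1 reports that the mean "in the first 48 hours after receiving ISB using liposomal bupivacaine was 12.0 +/- 2.3 in a previous study", in IV morphine equivalents. For the other arm, 4.2.2.2 expects patients to "use a similar average of 12.0 intravenous morphine equivalents in the first 48-hours following surgery".
- **Data already collected.** Appendix H has a field "Pre-surgical analgesics". Nothing in section 6 refers to it.

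**The concern.** A patient's opioid intake before surgery is a plausible strong predictor of intake in the two days after it. If the trial enrols both opioid-naive patients and regular users, part of the spread in 48 h consumption reflects who the patients were, not which block they received. An unadjusted comparison leaves that spread in the error term. With 36 per arm, the arms can also differ by several users through chance alone.

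Objective 2.2.2, the effect of the block on cumulative 48 h opioid use, is what is at stake. Its interval would be wider than it needs to be, and an observed difference would be harder to interpret if the arms turned out unequal in prior use. Adjustment chosen after the data are seen would look selective, so the choice belongs in the plan. The primary AUC outcome is not part of this point.

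**Working it through.** The plan gives no sample-size or precision calculation for opioid use. Section 6.2.2 states α and β but no detectable difference, so there is no plan figure to reproduce and a loss of precision cannot be turned into a loss of power. The check below asks how much the standard error (SE) could grow.

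**Inputs from the documents**
- Entry ceiling 40 mg oxycodone equivalents a day (3.2.4), so at most 2 × 40 = 80 mg over 48 h.
- Expected 48 h total 12.0 ± 2.3 IV morphine equivalents (4.2.2.1). The type of ± is not stated.
- SD 2.88 and SE 0.36 for the 48 h pain score from the same cited source (6.2.1).
- 36 patients per arm (6.3).

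**Assumptions, none given by the documents**
- 1 mg IV morphine corresponds to 1.5-3 mg oral oxycodone.
- The ± 2.3 is a standard error. Section 4.2.1.1 reports its pain figure from the same source as a standard error.
- 10-30% of enrolled patients are users, whose usual intake adds 40 or 80 mg per 48 h to their other use.
- The cited study's spread does not already include such users.

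**Step 1: baseline spread.** Implied reference n = (2.88/0.36)² = 64. SD = 2.3 × √64 = 18.4 mg IV morphine, which is 18.4 × 1.5 = 27.6 to 18.4 × 3 = 55.2 mg oxycodone.

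**Step 2: added spread.** If a share p of patients adds b mg, the added SD is b × √(p(1−p)).
- p = 0.10, b = 40: 40 × 0.300 = 12.0 mg.
- p = 0.30, b = 80: 80 × 0.458 = 36.7 mg.

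**Step 3: SE inflation** = √(1 + added SD² / baseline SD²).

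| Users and intake | Baseline SD 55.2 | Baseline SD 27.6 |
|---|---|---|
| 10%, 40 mg per 48 h | √(1 + 144/3047) = 1.02 | √(1 + 144/762) = 1.09 |
| 30%, 80 mg per 48 h | √(1 + 1344/3047) = 1.20 | √(1 + 1344/762) = 1.66 |

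The range is 2-9% at the mild end and 20-66% at the extreme end. In effective numbers, 36 per arm becomes 36/1.047 = 34 to 36/1.189 = 30 in the mild case, and 36/1.441 = 25 to 36/2.764 = 13 in the extreme case. This is the most that adjustment could recover.

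**Step 4: chance imbalance.** Exact binomial calculation with 36 per arm gives a probability of 17%, 30% and 37% that the arms differ by four or more users, for shares of 10%, 20% and 30%. A difference of four users moves the mean difference by 4/36 × 40 = 4.4 mg to 4/36 × 80 = 8.9 mg. For comparison, the ordinary 95% range of the mean difference without any user effect is ±1.96 × SD × √(2/36), which is ±12.8 mg (SD 27.6) to ±25.5 mg (SD 55.2).

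**Sensitivity.** If the ± 2.3 were an SD, the baseline spread would be eight times smaller. Even the mildest cell would then be about √(1 + 144/6.9²) = 2.0. The range in step 3 therefore depends on the standard-error reading. These figures are also in raw mg, whereas 6.2.2 plans geometric means. On a log scale large totals are compressed, but patients with little other use are moved further, so the raw-scale percentages do not carry over exactly.

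**The case against.** The case for leaving the plan alone is a fair one. An unadjusted comparison in a randomised trial is valid, and chance imbalance in prior use is already allowed for in the t test's standard error and error rate. Exclusions 3.2.4 and 3.2.7 narrow the group of users, and its size is unknown. The outcome is secondary. All of this stands, and it limits the point to precision.

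A reader might infer three stronger things that the documents do not support.

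1. *That a user will take up to 80 mg in 48 h whatever the block does.* No section says home opioids continue on a schedule. Section 5.3 describes opioids given as needed, and the users left after 3.2.7 may be taking them for the operated shoulder, which is the pain that the block treats.
2. *That usual intake is 2.2 to 4.4 times the expected total* (80 mg against 12.0 × 3 = 36 mg or 12.0 × 1.5 = 18 mg). This sets an individual's ceiling against a group mean. The mean also comes from a cited study whose entry criteria are not in the documents and which may have included similar patients.
3. *That imbalance will create a false difference or bias the comparison.* Randomisation balances prior use on average. The shifts in step 4 are smaller than ordinary chance variation under the same assumptions.

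What the objection does not answer is that the plan collects a baseline variable likely to predict this outcome and then sets it aside.

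**Conclusion.** The point holds as a missed gain in precision on the secondary opioid objective, with some vulnerability to chance imbalance at 36 per arm. It is not a bias or an invalid test. Its size cannot be fixed from the documents. If the ± 2.3 is a standard error with n of about 64, the conversion factor is 1.5-3, and usual intake adds to other use, the SE inflation runs from about 2-9% (10% users, 40 mg per 48 h) to 20-66% (30% users, all at the 80 mg ceiling). The upper figures need every user to be at the entry limit, so the lower part of the range is the safer expectation. The change is worth making because it costs almost nothing and has to be specified before the data are seen.

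**What to change.** Keep eligibility unchanged.

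1. **Appendix H:** record pre-operative opioid use as daily oxycodone equivalents, with zero entered explicitly for non-users.
2. **Section 6.2.2:** replace the unadjusted t test by a pre-specified linear model of log 48 h opioid use with treatment and pre-operative daily opioid use as covariate. Report the adjusted ratio of geometric means with a 95% CI. State the rule for patients with zero use, for example a fixed constant added to every total, because a geometric mean cannot be formed with zeros.
3. **Optional:** stratify the randomisation by pre-operative opioid use (yes/no). Once the covariate is in the model this adds little, and it can be omitted if enrolment has started.

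Two inconsistencies should be reconciled at the same time. Section 4.2.2.2 converts to oral codeine equivalents while 6.2.2 and Appendix H use oxycodone, and no conversion factor is given. Exclusion 3.2.4 and the Appendix A checklist also differ on chronic pain.

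The cost is one degree of freedom, one clarified form field and a short change to 6.2.2. No extra patients or visits are needed.

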4.0 Study Outcomes and Study Measures

4.1 Primary Outcome

- 4.1.1 The primary outcome of this study is the area-under-the-curve (AUC) of the mean visual analog scores numerical rating system (VAS-NRS) within the first 48 hours postoperatively. Pain levels (with shoulder movement) will be measured upon arrival to the PACU, at 6 hours, 12 hours, 24 hours, 36 hours, and 48 hours after surgery.
 - 4.1.1.1 The mean AUC48 of the liposomal bupivacaine ISB group was 136.4 with a standard error of 12.09.¹⁰
 - 4.1.1.2 There are no existing data to predict the mean AUC48 for ISB using plain bupivacaine +adjuvants, but we predict that this value will be within 20% of the mean AUC48 of the liposomal bupivacaine group, for a value of ~163.0.

4.2 Secondary Outcomes

- 4.2.1 Mean VAS-NRS pain score at 48 hours.
 - 4.2.1.1 For patients undergoing ISB with liposomal bupivacaine, the mean VAS pain score at 48 hours was 3.39 with a standard error of 0.37.¹⁰
 - 4.2.1.2 There are no existing data to predict the mean VAS pain score at 48 hours for patients undergoing ISB with plain bupivacaine + adjuvants, however a similar study using plain bupivacaine alone demonstrated a mean NRS (similar to VAS) pain score of 5.5 with standard error +/-0.5⁶. We expect the mean pain score to be slightly below this value, approximately 4.5.
- 4.2.2 Postoperative opioid consumption
 - 4.2.2.1 The mean rescue opioid consumption (in IV morphine equivalents) in the first 48 hours after receiving ISB using liposomal bupivacaine was 12.0 +/- 2.3 in a previous study.¹⁰
 - 4.2.2.2 We expect the patients treated with plain bupivacaine and adjuvants to use a similar average of 12.0 intravenous morphine equivalents in the first 48-hours following surgery. For the purpose of this study, we will convert IV morphine equivalents to oral codeine equivalents.
- 4.2.3 Satisfaction with surgical experience
 - 4.2.3.1 At the 48 hour mark, the patient's satisfaction with the surgical experience, satisfaction with pain control, and willingness to recommend the procedure to another patient will be assessed via Likert scale. Adverse events will also be evaluated.

Single Injection interscalene brachial plexus nerve block with adjuvants vs. Liposomal bupivacaine interscalene brachial plexus nerve block for total shoulder arthroplasty

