5.1 Study-Related Activities

Patients will be recruited from 2 sites- Wake Forest Baptist Health (Main Campus) and WFBH Davie. Patient involvement in the study will be initiated upon scheduling of their surgery with the Anesthesiology team. Eligible subjects will be identified via eligibility checklist (Appendix A) and contacted via phone call to inform them of the study and give them a brief overview. On the day of surgery, the consent for the study will be obtained after a pre-operative assessment and prior to initiating the regional block by the RAAPM team.

Single Injection interscalene brachial plexus nerve block with adjuvants vs. Liposomal bupivacaine interscalene brachial plexus nerve block for total shoulder arthroplasty

[figure not shown]
The study coordinator will then assign the patients will receive a study number, and the patient will be randomized by computer software algorithm to one of the study arms:

1. ISB using liposomal bupivacaine
2. ISB using plain bupivacaine with adjuvants

The study will be double blinded to patients, the perioperative nurses, the surgeon, and the study coordinators contacting the patient post-surgery.

To monitor our primary outcomes, patients will be asked to rate their pain level on a visual analog scale (Table 2, Appendix D) upon discharge from the PACU. Following discharge, they will continue to get every 12-hour pain assessments performed by research staff in person and/or over the phone (if they are discharged) until 48 hours have passed.

Table 2: Visual Analog Scale

Additionally, upon discharge, patients will be given a sheet to record the amount of narcotics and the time that they were used (Appendix G). At the 48-hour mark, patient's will be asked to rate their satisfaction with the procedure, and their willingness to recommend it, via Likert scale (Appendix E).

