Appendix E – Satisfaction Questionnaire

Subject Number: _____ DATE: ____ / ____ / ____ TIME: ____ : ____ AM/PM

Instructions: On the second day (48 hours) after surgery, please review the following questions, and choose the answer that best corresponds to each question regarding your experience.

| | Strongly Disagree | Disagree | Neutral | Agree | Strongly Agree |
|--------------------------------------------------------------------|----------------------|----------|---------|-------|-------------------|
| I believe my pain was well-controlled during after surgery. | | | | | |
| I would recommend this pain-control treatment to another patient. | | | | | |
| Have you had any itching since your surgery in your shoulder area? | YES | NO | | | |
| Have you had any nausea and/or vomiting since your surgery? | YES | NO | | | |

Single Injection interscalene brachial plexus nerve block with adjuvants vs. Liposomal bupivacaine
interscalene brachial plexus nerve block for total shoulder arthroplasty

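### The surgical-experience rating has no item on the study forms, and section 6.2.3 treats a five-point recommend item as binary

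*Combined protocol and SAP*

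**What the plan says.** Satisfaction appears in five places that matter here.

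- **Section 4.2.3.1** sets out what is measured at 48 hours: "the patient's satisfaction with the surgical experience, satisfaction with pain control, and willingness to recommend the procedure". It gives one response format for all three: "to another patient will be assessed via Likert scale".
- **Section 5.1** says that at 48 hours patients will "rate their satisfaction with the procedure, and their willingness to recommend it, via Likert scale (Appendix E"), so it names Appendix E as the instrument.
- **Section 6.2.3** gives the analysis: "Patient satisfaction will be assessed on POD#2 by 5-point Likert rating scale, and via a binary question of" whether the patient would recommend, worded as "would you recommend this pain relief regimen to the next patient". The answers are compared by Fisher's exact test at alpha 0.05.
- **Appendix E** is the questionnaire. It has four rows. Two use a five-level agreement scale: one on whether pain was well controlled, and one reading "I would recommend this pain-control treatment to another patient". The other two are yes/no rows on itching and on nausea or vomiting.
- **Appendix H** is the data collection form. Its satisfaction fields are "Likert Satisfaction #1" and a second Likert field numbered 2.

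**The concern.** The outcome section, the analysis section and the forms do not describe the same set of measurements. Two separate problems follow.

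First, the measure that gives 4.2.3 its title is not asked on the questionnaire and has no field on the data form. If the forms are used as they stand, a named secondary outcome will be empty at the end of the trial.

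Second, 6.2.3 plans to analyse a yes/no answer that the questionnaire does not request. An analyst following 6.2.3 would have to convert a five-level answer to two levels with no rule for doing so, in particular no rule on whether Neutral counts as yes or no.

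**Working it through.** The plan states no sample size, power or effect size for satisfaction, so there is no figure to reproduce. The check is an item-by-item comparison.

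| Measure | 4.2.3.1 | 5.1 | 6.2.3 | Appendix E | Appendix H |
|---|---|---|---|---|---|
| Surgical experience or procedure | Likert | Likert | not named separately | no row | no evident field |
| Pain control | Likert | not named | could be the five-point rating | five-point row | one Likert field |
| Willingness to recommend | Likert | Likert | binary | five-point row | one Likert field |

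The two Appendix H fields carry no label beyond their number. Matching them to the two five-point rows of Appendix E is an inference, though the natural one.

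**Surgical experience.** Section 4.2.3.1 names 3 Likert measures; Appendix E has 2 Likert rows and Appendix H has 2 Likert fields; 3 − 2 = 1 measure without an item. By elimination it is the surgical experience, because both Appendix E rows have a clear subject and neither is this one. The pain-control row cannot stand in for it, since 4.2.3.1 lists the two as distinct measures. Section 5.1 has the same gap: it refers to Appendix E for a rating of the procedure, and Appendix E has none.

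**Willingness to recommend.** Three places (4.2.3.1, 5.1, Appendix E) agree on a Likert format, and 6.2.3 alone says binary. The only yes/no rows in Appendix E concern side effects, so the number of binary recommend questions collected is 0, against 1 planned for analysis. No section gives a cut-point.

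**What a choice of cut could do.** In arm *i*, let *a_i* be the proportion answering Agree or Strongly Agree, and *n_i* the proportion answering Neutral.

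- Neutral counted as no: between-arm difference = *a_1* − *a_2*.
- Neutral counted as yes: between-arm difference = (*a_1* + *n_1*) − (*a_2* + *n_2*).
- Change due to the cut = *n_1* − *n_2*.

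The rate in each arm moves by that arm's Neutral share, but the difference between arms moves only by the gap between the two Neutral shares, and not at all if they are equal. The Fisher p-value can still change in that case. The documents give no figure for Neutral answers, so no size can be put on this.

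**The case against.** The strongest reply is that most of what the plan promises can still be delivered, and much of that reply is right.

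A reader might infer that willingness to recommend is not collected at all. It is: Appendix E asks it, in the format that 4.2.3.1 and 5.1 state. Only the binary form is absent.

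A reader might also infer that the whole of 6.2.3 is unworkable. It is not. Section 6.2.3 does not name the surgical experience; it refers to satisfaction on a five-point scale, which the pain-control row can supply. Fisher's exact test can be run on a 2 × 5 table, so both collected items can be compared without any cut. Only the binary clause has nothing to act on.

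A third tempting reading is that neither problem can be mended after 48 hours, or that a yes/no cut must be chosen with the results in view. The documents do not support this for the recommend item. Five levels hold more information than two, and an ordered analysis or a cut-point can be written into 6.2.3 at any time before unblinding. The point about lost data applies only to the surgical-experience rating.

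Finally, satisfaction is not among the secondary objectives in 2.2, which cover pain at 48 hours and opioid consumption. That limits the stakes. It does not remove the inconsistency, because 4.2 lists satisfaction as a secondary outcome and 6.2.3 assigns it a test.

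What remains after these replies is one outcome with no item and one analysis clause that does not match its form.

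**Conclusion.** The concern holds in two limited parts.

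1. The surgical-experience rating named in 4.2.3.1, and echoed in 5.1 as a rating of the procedure, has no row in Appendix E and no evident field in Appendix H. As written, 1 of the 3 stated satisfaction measures would have no data for any patient. A rating sought later would be a recalled one, not the planned 48-hour one.
2. Willingness to recommend is collected on five levels but is to be analysed as binary, with no cut-point. This is a format mismatch, repairable from the data the form already collects.

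The effect is confined to a secondary outcome with no power claim. The primary analysis and the sample size are unaffected.

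The conclusion assumes that Appendices E and H are the instruments actually used and that no other form asks about the surgical experience; the documents mention none. The Appendix H table is poorly laid out in the text available, so the finding rests mainly on Appendix E, whose table reads as complete.

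**What to change.** **Surgical experience.** Add one five-point row on it to Appendix E and a matching field to Appendix H. Alternatively, remove the measure from 4.2.3.1, retitle 4.2.3 and align 5.1. Either reconciles the documents; the choice depends on whether the investigators want the measure. If it is added after enrolment has begun, state from which patient onward it is available and report the number with data.

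**Willingness to recommend.** Amend 6.2.3 to analyse the existing five-point item as an ordered outcome, for example with a Wilcoxon rank-sum test, which uses the ordering that Fisher's exact test on five categories ignores. If a yes/no summary is wanted, define the dichotomy, including where Neutral falls, before unblinding. No new question is needed for either option.

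In the same edit, have 6.2.3 name each satisfaction item it analyses, label the two existing Appendix H fields by content, and use one description of what is being recommended, since 4.2.3.1, 6.2.3 and Appendix E each word it differently.

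The cost is at most one questionnaire row, one data field and a sentence or two of text. It adds no visit, because the questionnaire is already completed at 48 hours.
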